#### 4.4.3 Presentation of results

Frequency tabulations (number and percentages) will be provided with ADA negative/positive/unevaluable samples per analysis visit. In addition, these tables will be repeated by ADA participant category.

SGS	Statistical Analysis Plan	
ARGX-113-1905	Final analysis	Final 1.0 of 26APR2024

Frequency tabulations (number and percentages) will be provided overall on:

- participants per ADA participant category
- prevalence and incidence of ADA
- ADA unevaluable participants
- ADA baseline positive/negative samples

[figure not shown]
For details on the definitions, see the above section 4.4.2.1.

The above frequency tabulations will be repeated for NAb assay using the definitions as defined in section 4.4.2.2.

In addition, a cross-tabulation (number and percentages) will be provided of the overall NAb participant category (NAb positive participants and NAb not evaluable participants) versus the overall ADA participant category (treatment-unaffected ADA, Treatment-induced ADA, Treatment-boosted ADA, ADA Negative, ADA Unevaluable, Total).

ADA titer values against efgartigimod will be summarized by means of descriptive statistics by the ADA participant classification.

All available data on ADA and NAb against efgartigimod will be listed, showing also the sample status and participant classification.

## 5. SAFETY ANALYSES

All safety data will be presented for the Safety analysis set, unless mentioned otherwise.

## 5.1 ADVERSE EVENTS

#### 5.1.1 Available data

Adverse events will be coded into system organ classes (SOC) and preferred terms (PT) using the latest version of the MedDRA dictionary available at the time of the 1904 study database lock.

For each AE, start and stop date/times will be collected as well as severity, a seriousness flag, relationship to IMP, prednisone and procedures, action taken towards IMP and prednisone, outcome, and AE of special interest (AESI) category (infection).

The grade (severity) of AEs will be assessed by the investigator according to the National Cancer Institute (NCI) Common Terminology Criteria for Adverse Events (CTCAE) version 5.0.

#### 5.1.2 Derivation rules

Treatment-emergent adverse events (TEAE) are defined as AEs starting on or after any administration of IMP in 1905 up through 60 days after the last administration of IMP prior to the AE.

Post-treatment AEs are defined as AEs that start after the 60 days after the last IMP administration prior to the AE. AEs that start during the roll-over phase are also considered as post-treatment AEs

Based on their start date/time, AEs will be allocated to the phase in which they started. Each AE will therefore be reported in only one phase. Phases are defined in section 2.2.1. In case the AE start date/time is incomplete or missing, and the AE could consequently be allocated to more than one phase, a worst-case allocation will be done in following order:

- Treatment phase vs. roll-over phase: the AE will be allocated to the treatment phase unless the available parts of the AE start and stop date/time provide evidence for allocating to the roll-over phase.
- Treatment phase vs. follow-up phase: the AE will be allocated to the treatment phase unless the available parts of the AE start and stop date/time provide evidence for allocating to the follow-up phase.

A death case is defined as an AE with outcome 'fatal'.

An AE for which the IMP was discontinued is defined as an AE with action taken 'drug withdrawn'.

Treatment relatedness will be dichotomized as follows in tables:

- Treatment related: related, probably related, possibly related or missing
- Not treatment related: not related, unlikely related

Page 49 of 84

SGS	Statistical Analysis Plan	
ARGX-113-1905	Final analysis	Final 1.0 of 26APR2024

Adverse events of special interest will be defined using MedDRA system organ class 'Infections and infestations'.

Injection-related reactions (IRRs) will be defined as all AEs with MedDRA preferred terms that are listed in either:

- Hypersensitivity standardized MedDRA query (SMQ) (broad selection)
- Anaphylactic reaction (SMQ) (broad selection)
- Extravasation events (injections, infusions and implants) (SMQ) (broad selection), excluding implants

AND occurring within 48 hours of an administration, or within 2 days in case no AE start time is available. In case of partially missing AE start date, the AE will be considered as an IRR, unless the available parts of the AE start date provide evidence it did not occur within 48 hours of an injection.

Injection site reactions (ISR) will be defined as all AEs with a MedDRA high level term of "Injection site reaction", regardless of the time of AE onset relative to an administration.

AE onset and duration will be calculated as follows when start and stop dates are fully known:

- AE onset day (vs. roll over visit date) =
  - $\circ \quad AE \text{ start date} \geq date \text{ of first administration: AE start date} date \text{ of first } IMP \text{ administration} + 1 \text{ day}$
  - AE start date < date of first administration: AE start date date of first IMP administration
- AE duration (days) =
  - $\circ$  AE end date AE start date + 1 day
  - date of last contact AE start date + 1 day (when the AE start date is fully known but the AE is not resolved at the end of the study)

In this case the duration will be presented as ">x days".

SGS	Statistical Analysis Plan	
ARGX-113-1905	Final analysis	Final 1.0 of 26APR2024

Event rates per 100 participant years of follow-up (PYFU) will be calculated as 100\*number of events/PYFU, with:

• PYFU overall (in years) calculated as [the sum over all participants of the study duration calculated as (last phase end date – first phase start date + 1 day)]/365.25.

PYFU for TEAEs (in years) calculated as [the sum over all participants of all period durations during which an AE is considered to be treatment-emergent]/365.25.

• PYFU for post-TEAEs (in years) calculated as [the sum over all participants of all period durations during which an AE is considered to be post-treatment-emergent]/365.25.

Incidence rates per 100 participant years of follow-up (PYFU) will be calculated as 100\*number of participants with events/PYFU.

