An innovative drug is needed for the treatment of PV and PF that has a fast onset of action (eg, early disease control [DC, defined as the absence of new lesions and the start of healing of established lesions], complete clinical remission [CR, defined as the absence of new lesions and complete healing of established lesions] within weeks), a strong prednisone sparing effect, and a favorable safety profile. The late onset of action of rituximab is well-documented in the literature: in a meta-analysis reviewing 30 studies, DC was achieved by a mean of 7 to 8 weeks and CRmin by a mean of 6.5 months.

The antecedent trial ARGX-113-1904 intends to demonstrate that efgartigimod PH20 SC with an add-on therapy of oral prednisone at low doses would be a possible treatment modality for PV and PF that could lead to early disease remission at minimal prednisone dose. This trial has a treatment period of up to 30 weeks and provides a tailored dose regimen for participants by stopping investigational medicinal product (IMP) administration upon achieving CRmin (defined as the absence of new lesions and complete healing of established lesions while the participant receives minimal prednisone therapy of \leq 10 mg/day for at least 2 months [8 weeks]). *Note: when 10 mg/day is reached in ARGX-113-1904 or ARGX-113-1905, this dose level must be maintained for 8 weeks until CRmin has been achieved*.

This trial provides extension of efgartigimod PH20 SC treatment and retreatment options for participants who have been randomized to the efgartigimod PH20 SC treatment arm in ARGX-113-1904, and the first treatment of efgartigimod PH20 SC and retreatment options for participants who had been randomized to the placebo arm in ARGX-113-1904.

At the blinded rollover from ARGX-113-1904 into ARGX-113-1905, participants may be in different clinical stages of treatment. Participants may have achieved CRmin, participants may have achieved CR without meeting the minimal therapy criterion, participants may have achieved DC or end of consolidation (EoC, the time at which no new lesions have developed for a minimum of 2 weeks and approximately 80% of lesions have healed) without having achieved CR, participants may have had treatment failure or a flare after having achieved CRmin.

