9.2. Statistical Hypotheses

Not applicable. There is no specific statistical hypothesis that will be tested in this open-label study.

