**Table 2: Subperiod definition for AEs** 

EFG = efgartigimod (administration)

With 23:59 added as time part

P Repeat until the last subperiod

The end date/time of the last subperiod will correspond with the end date/time of the last phase as defined in Table 1. AEs starting during the roll-over phase will also be considered as post-TEAEs.

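### Every roll-over-phase AE is labelled post-treatment, so some events within the SAP's own 60-day window after 1904 efgartigimod enter the post-treatment rate

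*SAP*

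**What the plan says.** SAP 5.1.2 anchors treatment-emergent AEs to dosing in this study, "AEs starting on or after any administration of IMP in 1905", and gives them a tail: "up through 60 days after the last administration of IMP prior to the AE". The complementary category is general: "Post-treatment AEs are defined as AEs that start after the 60 days after the last IMP administration prior to the AE". That sentence is not limited to 1905 doses. The next one overrides it for one phase: "AEs that start during the roll-over phase are also considered as post-treatment AEs". The note under Table 2 in SAP 2.2.1 repeats the override: "AEs starting during the roll-over phase will also be considered as post-TEAEs".

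By Table 1 of the SAP, the roll-over phase exists only for participants who reached CRmin or CRoff in 1904 and had no IMP at the roll-over visit. The Protocol synopsis describes 1904 as "stopping investigational medicinal product (IMP) administration upon achieving CRmin", and Protocol 4.1 puts the 1905 baseline on the same date as the final 1904 visit.

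For reporting, SAP 5.1.2 computes post-treatment person-years from all time carrying the post-treatment label. SAP 5.1.3 makes the AE tables treatment-emergent only unless stated otherwise. SAP 2.1.1 requires at least one full or partial 1905 dose for the Safety set.

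**The concern.** Sixty days is the SAP's own choice of how long after a dose an AE still counts as treatment-emergent. The roll-over rule drops that test for the one group whose most recent dose was in 1904. Two participants with the same time since their last efgartigimod dose can therefore get opposite labels, depending only on which side of the roll-over visit that dose fell.

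TEAEs, AESIs and SAEs are the primary endpoint (Protocol 3). Infections are the AESI because efgartigimod lowers IgG (Protocol 8.4.8). At stake is whether the post-treatment rate describes only time beyond the SAP's window, and whether a serious event or infection a few weeks after a 1904 dose reaches the tables where a safety reader would look for it.

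**Working it through.** The documents give no figure to reproduce, so the check is a reading of the rules plus simple arithmetic.

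**Inputs**
- Window: 60 days after the last dose (SAP 5.1.2).
- Gap between the end of 1904 and the start of 1905: 0 days (Protocol 4.1).
- 1904 lasts at most 30 weeks (Protocol 8.3.10), and IMP stops at CRmin (Protocol 4.2).
- In 1905, dosing is weekly until CRmin, and assessments are done before dosing (Protocol 1.3, Table 1 footnotes). Assumption: 1904 worked the same way. The dose before the CRmin visit is then the last one, about 7 days earlier.
- The protocol expects recent CRmin at roll-over. PK/PD samples due 4 weeks after CRmin, and immunogenicity samples due at 4 and 8 weeks, are also taken in 1905 when CRmin fell in 1904 (Table 1 footnotes l and n).

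**Same exposure, different label.** Participant A had the last 1904 efgartigimod dose 7 days before roll-over, enters in CRmin, and has an infection 21 days after roll-over. That is 7 + 21 = 28 days from the last dose, labelled post-treatment. Participant B had the last dose 7 days after roll-over and an infection 28 days later. It is labelled treatment-emergent.

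**Time affected per participant.** d = max(0, 60 − gap), where gap is the number of days from the last 1904 dose to roll-over. With gap = 7, d = 53. With gap = 0, the extreme, d = 60.

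| Roll-over phase | d = 53 | d = 60 |
|---|---|---|
| 52 weeks (364 days) | 53/364 = 15% | 60/364 = 16% |
| 12 weeks, ended by flare (84 days) | 53/84 = 63% | 60/84 = 71% |

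**When the overlap arises.** Take roll-over at week 30, CRmin at week w and the last dose one week before CRmin. Then gap = 7 × (30 − w) + 7. CRmin at week 24, 26, 28 or 30 gives gaps of 49, 35, 21 and 7 days, so d = 11, 25, 39 and 53. The overlap is nil for CRmin before about week 30 − 53/7 = 22.4.

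**Effect on the post-treatment rate within the roll-over phase.** Suppose the rate is 50 per 100 person-years outside the window and r inside it (both assumed). For participants sharing the same d and phase length L, the reported rate is 50 + (r − 50) × d/L. With d = 53 and L = 364:
- r = 50: 50, no change
- r = 100: 50 + 50 × 0.146 = 57
- r = 150: 50 + 100 × 0.146 = 65

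Participants with longer gaps, and post-treatment time arising after 1905 dosing, would dilute this.

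**Where the events appear.** Tables 14.3.1.1.x and 14.3.1.2.x are marked SAF - ROLL and carry a post-treatment block, so the events are shown there. They are absent from the treatment-emergent tables on the Safety set for SAEs (14.3.1.4.x) and AESIs (14.3.1.12.x). The overall-AE block does not recover them, because SAP 5.1.3 defines it on the treatment and follow-up phases. Participants never dosed in 1905 are also outside the AE, SAE, fatal AE and AESI listings (16.2.7.1 to 16.2.7.3 and 16.2.7.5, all on the Safety set). Only the coding listing, 16.2.7.6, uses the Roll-over set.

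**The case against.** Tying TEAEs to IMP given in 1905 is a legitimate choice for a report on 1905. It matches the Safety set and the objective of treatment, extended treatment and retreatment. The protocol sets no TEAE window, so no protocol rule is broken. The analysis is descriptive: "There is no specific statistical hypothesis that will be tested in this open-label study". The overview and SOC/PT tables already show these events, including serious, grade 3 or higher, fatal and special-interest rows, with versions split by disease status at roll-over. Infections appear by preferred term. The 1904 analysis may already count this tail, which cannot be checked here. All of this stands, and it limits the point.

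Several stronger readings are tempting and are not supported:
- A reader might call these events on-drug. The participants had stopped IMP at CRmin. They are at most within 60 days of a dose.
- A reader might take the post-treatment rate as the trial's off-drug comparator. Neither document gives it that role, and Protocol 9.1.1 makes comparisons between prior treatment groups purely descriptive.
- A reader might conclude that the treatment-emergent rate is understated. Events and person-time are both left out, so the direction is unknown.
- A reader might suppose that many CRmin entrants are affected. The documents give neither their number nor when they reached CRmin.

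What the objection does not answer is the label itself. Time within 60 days of a dose fails the SAP's general definition of post-treatment, yet it is pooled into that rate.

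**Conclusion.** The inconsistency is real and lies inside the SAP. It concerns participants randomised to efgartigimod in 1904 who enter 1905 in CRmin or CRoff and are not dosed at roll-over. For placebo participants the label is right. It applies to AEs known to start in the roll-over phase, since events with incomplete dates default to the treatment phase.

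The size is bounded at about 53 days per affected participant, or 60 at the extreme. This rests on 1904 having used weekly dosing and predose assessment. How many participants or events are involved cannot be determined from the documents. The planned outputs do not hide the events altogether, but the treatment-emergent SAE and AESI tables omit them, and some participants fall outside the main AE listings. The point is worth correcting before the final analysis, but does not undermine the safety evaluation.

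**What to change.** In SAP 5.1.2 and Table 2:
- Keep the TEAE rows anchored to 1905 dosing.
- For participants who received efgartigimod in 1904 and have a roll-over phase, derive a sub-period from roll-over to the earlier of the last 1904 efgartigimod dose plus 60 days and the first 1905 dose.
- Tabulate AEs, SAEs and AESIs in that sub-period, with their own person-years, as a separate row on the Roll-over set, labelled as within 60 days of 1904 efgartigimod.
- Restrict post-treatment AEs and their person-years to time more than 60 days from any efgartigimod dose.
- Extend the AE, SAE, fatal AE and AESI listings to the Roll-over set.

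The cost is modest: one more derived sub-period, revised wording and additional table rows. The last 1904 dose date has to be brought in from the 1904 database, because SAP 2.1.2 refers to the actual treatment received in 1904, not to dosing dates. The new row must also be checked against the 1904 report so that no event is counted twice. No new data collection is needed.

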9.3. Sample Size Determination

Not applicable for this OLE trial.

9.4. **Populations for Analysis**

The following populations are defined:

Population	Description
Safety set	All participants who received at least 1 dose, or part of a dose, of IMP
Rollover set	All participants who rolled over from the ARGX-113-1904 study

The safety set is used for safety analysis (except for the analysis of C-GTI and GTI-SL). In general, the rollover set is used for efficacy evaluation (according to the treatment the participant was randomized to in the ARGX-113-1904 study). All details on the specific analysis of an endpoint in a specific population will be provided in the SAP.

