- Multiple treatment periods: assessments will be allocated to the first period that is possible based on the available parts of the assessments start and stop date/time.

SGS	Statistical Analysis Plan	
ARGX-113-1905	Final analysis	Final 1.0 of 26APR2024

A set of subperiods will be derived over the combined treatment and follow-up phase, to support the analysis of treatment-emergent adverse events (TEAEs) versus post-TEAEs.

Subperiod	Start	End
Treatment emergent 1	Treatment phase start date/time (see Table 1)	Date of first EFG where the next EFG is at least 61 days later + 60 days a
Post-treatment emergent 1	End date/time of previous subperiod + 1 minute	Start date/time of next subperiod - 1 minute
Treatment emergent 2	First EFG date/time following the start of previous post-treatment emergent subperiod	Date of first EFG where the next EFG is at least 61 days later + 60 days a
Post-treatment emergent 2	End date/time of previous subperiod + 1 minute	Start date/time of next subperiod - 1 minute
Etc. b		

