## 5.1.3 Presentation of results

Unless mentioned otherwise tables will present TEAEs only.

The TEAE tables will be presented for the treatment and follow-up phase combined.

Tables to be produced for the topline results (see list of outputs in section 8.1) will be presented overall and by disease status at roll-over in 1905. These tables will show data for PV+PF participants as well as for PV participants.

_	SGS	Statistical Analysis Plan	
A	ARGX-113-1905	Final analysis	Final 1.0 of 26APR2024

An overview table will show the number and percentage of participants with at least one event, the incidence rate per 100 PYFU, the number of events and the event rate per 100 PYFU for the following:

- TEAEs
- Treatment related TEAEs
- Serious TEAEs
- Serious treatment related TEAEs
- Serious prednisone related TEAEs
- TEAEs of grade 3 or above
- Treatment-related TEAEs of grade 3 or above
- TEAEs related to prednisone
- TEAEs related to study procedures
- TEAEs for which the IMP was discontinued
- TEAEs for which the IMP was interrupted
- TEAEs of special interest
- Treatment related TEAEs of special interest
- TE IRR events
- Serious TE IRR events
- TE ISR events
- Fatal TEAEs

The overview table will be repeated specifically for ISR events, omitting the records related to TEAEs of special interest, prednisone-related TEAEs, IRR and ISR events.

A summary table by MedDRA system organ class and preferred term will show the number and percentage of participants with at least one event, the incidence rate per 100 PYFU, the number of events and the event rate per 100 PYFU. Each AE record in the clinical database is considered as a distinct adverse event and is counted as such.

The overview and summary tables mentioned above, will present:

- TEAEs
- post-TEAEs
- overall AEs (i.e., all AEs in the treatment + follow-up phase)

SGS	Statistical Analysis Plan	
ARGX-113-1905	Final analysis	Final 1.0 of 26APR2024

Separate tables will be prepared by MedDRA system organ class and preferred term showing the number and percentage of participants with at least one event, the incidence rate per 100 PYFU, the number of events and the event rate per 100 PYFU for the following:

- Most common TEAEs (>=5% in the Total group)
- Treatment related TEAEs
- Serious TEAEs
- Serious treatment related TEAEs
- Serious prednisone related TEAEs
- TEAEs of grade 3 or above
- Treatment-related TEAEs of grade 3 or above
- TEAEs related to prednisone
- TEAEs related to study procedures

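### Injection-related reaction rates per 100 participant-years count up to 60 injection-free days after each course, so they fall as courses get shorter; add a rate per 100 administrations

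*SAP*

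**What the plan says.** SAP 5.1.2 treats an adverse event as treatment-emergent if it starts on or after a dose, "up through 60 days after the last administration of IMP prior to the AE". SAP Table 2 (section 2.2.1) turns this into subperiods and gives the end of each as "Date of first EFG where the next EFG is at least 61 days later + 60 days". Below that table the length is capped: "The end date/time of the last subperiod will correspond with the end date/time of the last phase as defined in Table 1".

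The person-time for treatment-emergent rates (PYFU) is "the sum over all participants of all period durations during which an AE is considered to be treatment-emergent", divided by 365.25. Event rates are events, and incidence rates are participants with an event, per 100 PYFU.

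To qualify as an IRR, an event needs a preferred term from one of three standardised MedDRA queries, with the further condition "AND occurring within 48 hours of an administration, or within 2 days in case no AE start time is available". A partly missing start date is resolved in favour of an IRR unless the known parts rule it out. ISRs are defined by MedDRA high level term alone, whatever the delay since the injection.

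SAP 5.1.3 gives participants, percentages, event counts and both rates for TE IRR, serious TE IRR and TE ISR, in the overview and in tables by system organ class and preferred term. Section 8.1 repeats the overview (Table 14.3.1.1.2) and the ISR tables (14.3.1.16.2 and 14.3.1.16.4) by disease status at roll-over. No other denominator is offered.

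**The concern.** For general adverse events, numerator and denominator share one window. For IRRs they do not: the numerator is tied to the 48 hours after an administration, while the denominator runs on for up to 60 days after dosing stops.

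The dilution depends on course length, which the design varies. Dosing stops at CRmin (Protocol Table 1, footnote t). A participant who enters in CR already at 10 mg/day may need fewer than 8 weekly doses. One who starts to taper from 0.5 mg/kg faces at least 2 weeks at 20 mg, 3 weeks from 17.5 to 12.5 mg and 8 weeks at 10 mg, which is 13 weeks (Protocol Table 4 and section 4.1). Retreatment may be as short as 4 weeks.

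Safety is the primary objective, and Protocol 9.5.5 asks for safety by status at entry. The rate per 100 PYFU is the only exposure-adjusted figure in these tables. Between strata it could mix tolerability with course length.

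**Working it through.** There is no planned figure to reproduce. Protocol 9.3 says of sample size "Not applicable for this OLE trial", and neither document states an expected IRR rate. The check is person-time arithmetic.

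**Inputs.** Weekly dosing until CRmin and a last planned dose at week 52 (Protocol Table 1, footnote t); a 4-week minimum for a new course (SAP 1.2); a 60-day tail (SAP 5.1.2 and Table 2); 8 weeks, or 56 days, of follow-up after week 52 (Protocol section 8). Course lengths between 4 and 52 doses are assumed, because the documents give none.

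**Formulas** for one course of k weekly doses:
- Treatment-emergent days = 7(k−1) + 1 + tail.
- Weekly-dosing days = 7k.
- Reported share = 7k / treatment-emergent days, if no IRR starts after the last dosing interval.

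With a 60-day tail the excess is 54 days whatever k is, because 7(k−1) + 61 − 7k = 54. With 56 days it is 50. A fixed excess weighs most on short courses.

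| Doses | Tail (days) | Dosing days | Treatment-emergent days | Share |
|---|---|---|---|---|
| 4 | 60 | 28 | 82 | 0.34 |
| 4 | 56 | 28 | 78 | 0.36 |
| 8 | 60 | 56 | 110 | 0.51 |
| 12 | 60 | 84 | 138 | 0.61 |
| 26 | 60 | 182 | 236 | 0.77 |
| 52 | 56 | 364 | 414 | 0.88 |

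**In rate units**, assuming 5 IRRs per 100 administrations:
- 4 doses: 100 × 0.2 / (82/365.25) = 89 per 100 PYFU.
- 52 doses: 100 × 2.6 / (414/365.25) = 229 per 100 PYFU.
- Over weekly-dosing time, both give 100 × 0.05 / (7/365.25) = 261.

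**What softens it.**
- Pooling: equal numbers of 12-dose and 52-dose participants give (84+364)/(138+414) = 448/552 = 0.81.
- Early retreatment: two 8-dose courses, the second starting 30 days after the last dose of the first, give 112/189 = 0.59, against 112/220 = 0.51 with two full tails.
- Early last contact: 4 doses with a 28-day tail give 28/50 = 0.56.

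**ISRs.** Let the rate in the excess days be a fraction f of the on-treatment rate. The share becomes (7k + f × excess) / treatment-emergent days. At f = 0.25 this is (28 + 13.5)/82 = 0.51 for 4 doses and (364 + 12.5)/414 = 0.91 for 52. The gradient vanishes only at f = 1. The documents give no information on f.

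**The case against.** **The results are descriptive.** Protocol 9.2 says "There is no specific statistical hypothesis that will be tested in this open-label study", the measure is labelled follow-up rather than exposure, and counts and percentages are unaffected. All true. It lowers the stakes but does not remove the mismatch in the one adjusted figure.

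**Weekly-dosing time is also a chosen reference.** About 5 of every 7 dosing days cannot contain an IRR either. That share is the same for every weekly schedule, though, so it does not distort comparisons. The tail share does change with course length.

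**The figures are extremes.** They assume uniform single courses. One might infer from 0.609/0.879 = 0.69 that 12-week groups will show rates 31% below 52-week groups. The documents do not support that as a forecast: real strata mix course lengths, and tails can be shorter.

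**ISRs may start late.** A reader might infer that no ISR can arise in the tail. The SAP sets no onset limit and gives no latency data, so this remains a likely inference.

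**Discontinuation and interruption.** It is tempting to extend the point to "TEAEs for which the IMP was discontinued" and to the interruption row, on the ground that stopped treatment cannot be withdrawn. The documents do not bear this out. SAP 2.2.1 keeps a temporary stop for an adverse event inside the same treatment period, and Protocol Appendix 11 has treatment interrupted during COVID-19. An event starting during such a hold, more than 7 days after the last dose, could still be recorded as leading to withdrawal. A dosing-time denominator would then miss its time at risk.

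**The data are already there.** Administrations are tabulated overall and by roll-over status (Tables 14.1.2.5.1 and 14.1.2.5.2), so a reader could work out the ratio. This stands, and it is why the remedy costs little.

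**Conclusion.** The point holds for IRRs and serious IRRs as a matter of definition, and probably for ISRs. Under constant risk per weekly administration and one course each, the reported rate ranges from about 34% of the weekly-dosing rate (4 doses) through 61% (12) to 88% (52, with a 56-day tail). These are illustrative bounds, and the actual effect depends on a mix of course lengths that the documents do not give. Comparisons by roll-over status or prior arm can differ for no reason other than course length. Whether course lengths do differ by prior arm is not stated.

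A reader might go further and conclude that the 60-day person-time is wrong in general. It is not: for other treatment-emergent events the numerator uses the same window. The SAP also gives no sufficient ground for changing the denominator of the discontinuation and interruption rows. This is a cheap improvement to reporting and leaves the rest of the safety analysis as planned.

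**What to change.** In SAP 5.1.2, define an additional rate: 100 × number of treatment-emergent events / number of administrations in 1905, using the count already derived in 3.4.2. In 5.1.3, show it for the TE IRR, serious TE IRR and TE ISR rows of the overview and for the IRR and ISR tables. Give it overall, and by roll-over status where those tables are already split that way.

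Keep the participant counts, percentages and both per-PYFU columns; an event rate per administration does not replace participant incidence.

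Add a footnote that the per-PYFU rates in these rows include time without injections. State how loading doses are counted: Protocol Table 3 has them given at separate sites and only for some entry statuses and new courses, so one administration might not mean the same number of injections in every stratum.

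Leave the IMP discontinuation and interruption rows as they are. The cost is one extra column, a footnote and a counting rule, with no new data.
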